8.4. Weight and Vital Signs

Vital signs, including temperature, heart rate, respiration rate, blood pressure (BP), and weight are to be measured. Vital signs should be measured after the patient has been sitting for 3 to 5 minutes.

8.5. Concurrent Medications

All prescription and non-prescription medications and therapies, including pharmacologic doses of vitamins, herbal medicines, or other non-traditional medicines, taken from 28 days before the first dose of SL-901 through the EOT visit. On PK sample collection days, both the date and time of concomitant medications and therapies should be recorded.

8.5.1. Prohibited Concurrent Medications

The following medications are prohibited during the study:

- Any investigational agent or device other than SL-901, including agents that are commercially available for indications other than the patient's solid tumor that are under investigation for the treatment of solid tumors.
- Any anti-neoplastic treatment with activity against solid tumors other than SL-901.

8.5.2. Permitted Concurrent Medications

Medications and treatments other than those specified in [Section 8.5.1](#), including palliative and supportive care for disease-related symptoms (e.g., appetite stimulants, stimulants [modafinil], anti-cachexia therapy [fish-oil supplements], anti-depressants, opiate and non-opiate analgesics, antibiotics, selective use of corticosteroids, and, as indicated below, anti-emetic and anti-diarrheal agents and hematopoietic growth factors), are permitted during the study. In case of hyperglycemia grade 3 or higher, treatment with Metformin is permitted.

Patients should be closely monitored, and treatment is to be instituted for disease-related symptoms, as appropriate.

8.5.3. Additional Important Considerations

Clinical drug-drug interaction studies with SL-901 have not been performed.

Concomitant therapy with drugs that are strong inhibitors or inducers of CYP3A and induce CYP2B6 (e.g., clarithromycin, itraconazole, phenytoin, rifampicin), may cause SL-901 toxicity or lack of efficacy. In addition, drugs that are substrates of CYP3A (e.g., drugs include amlodipine, amitriptyline, and carbamazepine) may reach toxic levels of exposure due to inhibition by SL-901, and therefore caution with use of such drugs is advised.

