5.2. Exclusion Criteria

Patients meeting any of the following criteria will be excluded from the study:

1. Received an investigational anticancer drug within 4 weeks of the first planned SL-901 dose.
2. Received major surgery, radiotherapy, or immunotherapy within 4 weeks of C1D1. Localized palliative radiotherapy is permitted for symptom control.
3. Received chemotherapy regimens with delayed toxicity within 4 weeks (6 weeks for prior nitrosourea or mitomycin C) of C1D1.
4. Received chemotherapy regimens given continuously or on a weekly basis which have limited potential for delayed toxicity within 2 weeks of C1D1.

5. Clinically significant, unresolved toxicity from previous anticancer therapy \geq Grade 2 (except alopecia), as determined by the Investigator using the National Cancer Institute Common Terminology Criteria for Adverse Events (NCI CTCAE), version 5.0.
6. Presence of active gastrointestinal disease or other condition that will interfere significantly with the absorption, distribution, metabolism, or excretion of drugs.
7. Left ventricular ejection fraction $<50\%$.
8. Corrected QT interval (based on Fridericia's formula) >450 msec.
9. Type 1 or 2 diabetes mellitus requiring medication. (In Part 1b, patients with type 2 diabetes mellitus controlled by medication, as indicated by a glycated hemoglobin of $\leq 7.5\%$ are eligible.)
10. Known active human immunodeficiency virus, hepatitis B, or hepatitis C infection.
11. Ongoing systemic bacterial, fungal, or viral infection.
12. History of interstitial pneumonitis.
13. Absolute neutrophil count (ANC) $<1.5 \times 10^9/L$.
14. Hemoglobin <10 g/dL.
15. Aspartate aminotransferase (AST) or alanine aminotransferase (ALT) $>2.5 \times$ the upper limit of normal (ULN).
16. Known hypersensitivity or allergy to the active ingredient or excipients of SL-901.
17. Breast-feeding females.

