6.4.1. Dose-Escalation Scheme in Part 1a

Initially, up to 3 patients are to be enrolled in each cohort. After 3 patients complete C1 and have safety evaluations performed through C2D1, and if:

- None of these 3 patients experience a DLT in either dosing schedule, then enrollment of the next cohort may commence.
- 1 of 3 patients within a cohort experiences a DLT, then up to 3 additional patients are to be enrolled sequentially at that dose level in that dosing schedule. If none of the additional 3 patients experience a DLT (i.e., 1 of 6 patients has a DLT), then enrollment at the next scheduled dose may commence.
- ≥ 2 patients within a cohort experience a DLT, then the DLT dose level will have been reached and the previous lower dose level will be considered the MTD for that dosing schedule.

Note that enrollment in the next dose cohort can begin only when the last patient enrolled in the current dose cohort completes C1 and is assessed for DLT, provided that <2 patients in the current dose cohort experienced a DLT.

Although decisions regarding dose-escalation will be made based on review of data from C1, safety data will also be collected from all patients continuing treatment and this will be reviewed periodically. Any detected cumulative toxicity may require later dose reductions or other action as appropriate, including further refinement of the MTD.

Based on evaluation of the safety and tolerability data, it may be decided that escalation to the next dose level should be more conservative than specified and that the next higher dose will be an intermediate dose level.

An MTD will be identified for each dosing schedule.

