6.4.3. Operational Characteristics of Dose-Escalation

All dose-escalation steps and schedule recommendations will be made by a review committee, comprised of the study Investigators and Sponsor representatives, who will review the available safety and other relevant data to inform the decision. Refer to the Data Safety Review Charter (DSRC) for further details.

A sample size of at least 3 patients in each cohort, expanding to 6 patients in the event of a marginal DLT rate (33%), is a conventional approach in dose-escalation studies of investigational oncologic agents.

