8.8. Pharmacokinetics

See [Table 8](#) for the PK assessment schedule.

A large black rectangular box redacting content from the original document.

8.9. **Electrocardiogram**

Twelve-lead ECGs will be performed 5 to 10 minutes before the PK sample is collected and analyzed locally in triplicate over 5 minutes (\pm 5 minutes) contemporaneously with selected PK sampling time points, as indicated in [Table 8](#).

Table 8: Time Points for Pharmacokinetic and Electrocardiogram Assessments

Timepoint	Run-in Serial PK Sampling and ECGs (3-7 days before C1D1; Part 1a only)		Steady State Sampling and ECGs (C1D8; C1D22; C2D1; C2D8; C2D15; C2D22; Cycles 3 and beyond D1, D15 Part 1a and Part 1b)		Serial PK Sampling and ECGs (C1D15 Part 1a and Part 1b)	
	PK	ECG¹	PK	ECG¹	PK	ECG¹
Predose	X	X	X	X	X	X
60 minutes postdose	X	X	--	--	X	X
2 hours postdose	X	X	--	--	X	X
4 hours postdose	X	X	--	--	X	--
6 hours postdose	X	--	--	--	X	--
8 hours postdose	X	--	--	--	X	--
10 hours postdose	X	--	--	--	X	--
12 hours postdose	X	--	--	--	X	--
24 hours postdose	X	X	--	--	X	X
48 hours postdose	X	X	--	--	--	--
72 hours postdose	X	X	--	--	--	--

C = cycle, D = day, ECG = electrocardiogram, PK = pharmacokinetic

¹. ECG should be performed as triplicates and at least 5-10 minutes before the PK sample is collected.

8.10. **Pharmacodynamics**

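### The protocol warns that strong CYP3A inhibitors and inducers may make SL-901 toxic or ineffective, but it permits them, and a patient taking one counts toward the 2-DLT rule like any other

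*Protocol*

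**What the plan says.** **The warning.** Protocol 8.5.3 states: "Clinical drug-drug interaction studies with SL-901 have not been performed". It then says that certain drugs "may cause SL-901 toxicity or lack of efficacy", giving clarithromycin, itraconazole, phenytoin and rifampicin as examples. Its description of the class is garbled: it joins strong inhibition or induction of CYP3A with induction of CYP2B6. The section's advice of caution comes in the next sentence, which is about drugs that are CYP3A substrates.

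**The medication rules.** Protocol 8.5.1 has two entries. One covers investigational agents and devices. The other reads "Any anti-neoplastic treatment with activity against solid tumors other than SL-901". Protocol 8.5.2 permits everything not listed in 8.5.1, and its examples include "antibiotics, selective use of corticosteroids, and, as indicated below, anti-emetic and anti-diarrheal agents and hematopoietic growth factors), are permitted during the study".

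**Entry.** None of the 17 exclusions in Protocol 5.2 names a CYP3A drug. Two come near:
- Criterion 6 covers gastrointestinal disease or another condition that significantly disturbs drug absorption, distribution, metabolism or excretion.
- Criterion 11 is "Ongoing systemic bacterial, fungal, or viral infection".

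**Counting.** Protocol 6.4.2 makes a patient evaluable on at least 75% of Cycle 1 doses plus assessments through C2D1, or on discontinuing because of a DLT. SAP 7.3 adds the full run-in dose. Under Protocol 6.4.1, if two or more patients in a cohort have a DLT, "then the DLT dose level will have been reached and the previous lower dose level will be considered the MTD".

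**The concern.** The MTD, the regimen and the PK profile are primary objectives, and each dose is judged on 3 to 6 patients. A strong inhibitor could raise SL-901 exposure and produce a DLT that the dose alone would not. That DLT triggers expansion and leaves only one more needed to reject the dose. A strong inducer could lower exposure and make a dose look tolerable.

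PK is affected too. One primary PK endpoint compares the first dose with steady state, so an interacting drug started between the run-in and C1D15 would be confounded with that change.

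There is also a patient-safety reason that needs no effect size: the plan permits a combination that it says itself may be toxic.

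**Working it through.** **1. Does anything visible bar these drugs?**
- Criterion 6 speaks of a disease or condition, not of a medicine.
- Criterion 11 removes some users of anti-infectives at entry. It does not reach prophylaxis, an infection arising on study, or phenytoin.
- Protocol 7.3 allows discontinuation when a patient needs a prohibited medication. These drugs are not prohibited, so it does not apply.

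The answer is no.

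**2. How is a user counted?** Evaluability and replacement depend on doses taken and assessments completed, with no concomitant-medication ground. A toxicity caused by raised SL-901 exposure still has a reasonable possibility of being caused by SL-901, so it meets the DLT definition. The sponsor cannot reverse an investigator's finding of related (6.4.2). A user is therefore counted like anyone else.

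**3. Size.** The plan makes no formal sample-size calculation, so it has no figure to reproduce. The inputs below are assumptions, apart from the escalation rule in 6.4.1:
- p: DLT risk of a non-user.
- q: DLT risk of a user.
- f: proportion of patients using such a drug (2%, 5% or 10%).

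The average risk per patient is r = f·q + (1 − f)·p. A dose is passed with 0 of 3 DLTs, or with 1 of 3 followed by 0 of 3:

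P(escalate) = (1 − r)³ + 3r(1 − r)²·(1 − r)³, and P(stop) = 1 − P(escalate).

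Example with p = 0.10, q = 0.50, f = 0.05: r = 0.025 + 0.095 = 0.12. P(escalate) = 0.6815 + 0.36 × 0.5277 = 0.8715, so P(stop) = 12.85%. With no users, r = 0.10 and P(stop) = 9.39%. A simulation of 2 million cohorts with the same inputs gave 12.83%.

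| Scenario | No users | f = 2% | f = 5% | f = 10% |
|---|---|---|---|---|
| Inhibitor, p = 0.10, q = 0.30: stop | 9.39% | 10.05% | 11.08% | 12.85% |
| Inhibitor, p = 0.10, q = 0.50: stop | 9.39% | 10.73% | 12.85% | 16.64% |
| Inhibitor, p = 0.20, q = 0.30: stop | 29.14% | 29.57% | 30.22% | 31.31% |
| Inhibitor, p = 0.20, q = 0.50: stop | 29.14% | 30.44% | 32.40% | 35.67% |
| Inducer, p = 0.30, q = 0.10: escalate | 49.43% | 50.25% | 51.49% | 53.58% |
| Inducer, p = 0.40, q = 0.10: escalate | 30.93% | 31.91% | 33.42% | 36.02% |

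At f = 5% the shifts run from 30.22 − 29.14 = 1.1 points to 12.85 − 9.39 = 3.5 points.

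**4. A single affected cohort.** Suppose exactly one inhibitor user is among the first 3 and none is in any expansion. Then P(0 DLT) = (1 − q)(1 − p)² and P(1 DLT) = q(1 − p)² + (1 − q)·2p(1 − p). With p = 0.10:
- q = 0.30: 0.567 + 0.369 × 0.729 = 0.836, so stopping is 16.4%.
- q = 0.50: 0.405 + 0.495 × 0.729 = 0.766, so stopping is 23.4%.

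The chance of at least one user among the first 3 is 1 − (1 − f)³, which is 5.9%, 14.3% or 27.1% for f = 2%, 5% or 10%.

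**5. How much the counting rule matters.** Suppose the user has the only DLT in the first 3, and p = 0.10. If that patient counts, P(escalate) = 0.9³ = 0.729. If replaced by a non-user, it is 0.9 + 0.1 × 0.9³ = 0.973.

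Replacing only users without a DLT would be a poor rule. With p = 0.10, q = 0.50, f = 0.05 and non-user replacements, r = 0.025 + 0.025 × 0.10 + 0.095 = 0.1225. Stopping then rises from 12.85% to 13.31%. The rule discards reassuring inhibitor users and keeps the alarming ones.

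**The case against.** The best defence is that this is a deliberate choice with several layers of review behind it.
- Table 8 gives full profiles at "Run-in Serial PK Sampling and ECGs (3-7 days before C1D1; Part 1a only") and at C1D15, with predose samples between and after.
- Protocol 8.5 records co-medication times on PK days.
- The causality factors in 8.2.2 include both concomitant medication and the drug's pharmacology.
- A committee takes the escalation decisions, "who will review the available safety and other relevant data to inform the decision" (6.4.3), and 6.4.1 lets it choose an intermediate dose.
- SAP 7.4.1 reports weekly cohort reviews.

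All of this stands as detection. None of it keeps a patient off the combination. The concomitant-medication factor asks whether the other drug caused the event, which is a different question from whether it raised SL-901 exposure.

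Other points also stand. A warning without a prohibition is not a contradiction. The advice of caution could, on a loose reading, extend to inhibitors and inducers, though the grammar favours substrates. Protocol 1.2, 2.1.2.1, 6.5, the text of 8.8 and 9.3.6, SAP 12.3 and the Data Safety Review Charter are not visible. Any of them could hold a handling rule or show how much CYP3A matters for SL-901. Part 1a has stopped and Part 1b never started (SAP 4), so the design change matters only if SL-901 is dosed again.

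A reader might infer that the plan leaves such a patient's place in the DLT count undefined. It does not: 6.4.2 and SAP 7.3 count the patient by default. What is not visible is a specific rule for this situation.

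**Conclusion.** The point holds as a low-cost improvement. The visible text warns of the interaction, permits the drugs, and counts users by the general rule. The likely effect on escalation is modest: about 1 to 3.5 points at an assumed 5% use, with assumed DLT risks of 10% to 40% in non-users and 10% to 50% in users. These figures are illustrations, not estimates.

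Two stronger readings are not supported. The 16.4% to 23.4% stopping chance describes one specific cohort make-up and is not the expected effect. And nothing in the documents shows that any Part 1a patient took such a drug, so it cannot be said that a DLT, the MTD or a PK result was distorted.

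**What to change.** **For any further SL-901 dosing:**
- Prohibit strong CYP3A inhibitors and inducers in Protocol 8.5.1, with a matching washout in 5.2, from before the run-in dose through at least C2D1. The sponsor sets the drug list and the interval.
- Make 8.5.2 and 8.5.3 consistent with this, and reword the CYP3A/CYP2B6 phrase so that the class is clear.
- State in 6.4.1 how a patient who takes such a drug anyway counts toward the 2-DLT rule. The rule should be set in advance and should not depend on whether a DLT occurred: all such patients count, or all are replaced.

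**For the stopped Part 1a:** flag patients who took such a drug through C2D1 in Listings 16.2.7.3, 16.2.9.1 and 16.2.9.2, and note any affected DLT or PK value in the report. The PK part is needed only if Protocol 9.3.6 and SAP 12.3 do not already cover it.

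**Cost:** a short amendment to 5.2, 6.4.1 and 8.5, and one flag built from data already collected. A few patients would have to switch medicine or would be ineligible.

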8.6. Pregnancy

Pregnancies occurring in the patient or patient's partner while the patient is receiving study drug or within 30 days after the patient's last dose of study drug will not be considered serious, but are to be reported as IMEs using the same procedures as for SAEs described in [Section 8.2.1](#).

Study drug must be discontinued immediately in the event of a pregnancy. The patient should be referred to an obstetrician/gynecologist experienced in reproductive toxicity for further evaluation and counseling.

The Investigator will follow the patient until completion of the pregnancy and must notify the Sponsor of the outcome. The Investigator will provide this information as a follow-up to the initial report.

If the outcome of the pregnancy meets the criteria for immediate classification as an SAE (i.e., spontaneous abortion [any congenital anomaly detected in an aborted fetus is to be documented], stillbirth, neonatal death, or congenital anomaly), then the Investigator should report it as such. Furthermore, all neonatal deaths that occur within 30 days of birth should be reported, without regard to causality, as SAEs. In addition, any infant death after 30 days that the Investigator suspects is related to the in utero exposure to the study drug should also be reported.

[figure not shown]
8.7. Tumor Assessments

Tumor assessment by will occur at Screening (for identification of baseline disease) and after every 2 cycles of treatment thereafter. Response will be evaluated using Response Evaluation Criteria in Solid Tumors (RECIST) v1.1 ([Eisenhauer 2009](#)).

After completion of the EOT visit, patients will then be followed every 90 days for survival status for 12 months. The survival follow-up may be by telephone contact. If the patient discontinued study drug for reasons other than progressive disease, disease assessments should continue to be performed on an every 8-week basis (± 1 week) through 6 months after the first study drug dose and then on an every 90-day basis or until, in the judgment of the Investigator, there is evidence of relapsed or progressive disease.

8.8. Pharmacokinetics

See [Table 8](#) for the PK assessment schedule.

A large black rectangular box redacting content from the original document.

8.9. **Electrocardiogram**

Twelve-lead ECGs will be performed 5 to 10 minutes before the PK sample is collected and analyzed locally in triplicate over 5 minutes (\pm 5 minutes) contemporaneously with selected PK sampling time points, as indicated in [Table 8](#).

Table 8: Time Points for Pharmacokinetic and Electrocardiogram Assessments

Timepoint	Run-in Serial PK Sampling and ECGs (3-7 days before C1D1; Part 1a only)		Steady State Sampling and ECGs (C1D8; C1D22; C2D1; C2D8; C2D15; C2D22; Cycles 3 and beyond D1, D15 Part 1a and Part 1b)		Serial PK Sampling and ECGs (C1D15 Part 1a and Part 1b)	
	PK	ECG¹	PK	ECG¹	PK	ECG¹
Predose	X	X	X	X	X	X
60 minutes postdose	X	X	--	--	X	X
2 hours postdose	X	X	--	--	X	X
4 hours postdose	X	X	--	--	X	--
6 hours postdose	X	--	--	--	X	--
8 hours postdose	X	--	--	--	X	--
10 hours postdose	X	--	--	--	X	--
12 hours postdose	X	--	--	--	X	--
24 hours postdose	X	X	--	--	X	X
48 hours postdose	X	X	--	--	--	--
72 hours postdose	X	X	--	--	--	--

C = cycle, D = day, ECG = electrocardiogram, PK = pharmacokinetic

¹. ECG should be performed as triplicates and at least 5-10 minutes before the PK sample is collected.

8.10. **Pharmacodynamics**

9. STATISTICAL CONSIDERATIONS

9.1. Statistical Basis for Sample Size

No formal sample size calculation is required in this Phase 1 dose-escalation and dose expansion study. For each dosing schedule, 3 to 6 patients are to be enrolled in each dose-escalation cohort in Part 1a. Up to 60 patients in total are to be enrolled in the dose-escalation cohorts.

The total number of patients to be enrolled is dependent upon the observed safety profile, which will determine the number of patients per dose cohort, as well as the number of dose-escalations required to achieve the MTD.

A sample size of at least 3 patients in each cohort, expanding to 6 patients in the event of a marginal DLT rate (33%), is a conventional approach in dose-escalation studies of investigational oncologic agents.

Six to 12 patients in each expansion cohort (up to 4 cohorts) are to be enrolled in Part 1b.

9.2. Populations for Analysis

The intent-to-treat (ITT) principle will be followed for the safety and efficacy populations. This is defined as all patients enrolled into the study and who received any amount of SL-901.

As warranted by the data, efficacy also may be assessed in a per-protocol population, defined as all patients who receive at least 1 cycle of treatment, have at least 1 post-baseline efficacy assessment, and have no major protocol violations, as defined by the Sponsor.

PK analyses will be performed on the PK population, defined as all patients who receive any amount of SL-901 and have sufficient data for PK analysis.

9.3. Statistical Analysis Plan

9.3.1. Patient Disposition

Data tabulations will summarize the number of patients:

- Enrolled
- At least 1 SL-901 dose received
- Evaluable for safety and efficacy
- Protocol violations
- Withdrawn from study due to:
 - AE
 - Investigator request
 - Withdraw consent
 - Lost to Follow-up
 - Other reasons

9.3.2. Demographic and Baseline Characteristics

Demographic and baseline characteristics of patients will be summarized using descriptive statistics, including:

- Age
- Sex
- Race
- Ethnicity
- Baseline ECOG performance status
- Primary diagnosis
- Disease stage at diagnosis and Baseline
- Prior therapies, including systemic therapies, radiation, and surgeries
- Other baseline characteristics

9.3.3. Concurrent Medications

The number and proportion of patients in the safety analysis set using different concomitant medications will be tabulated and summarized by World Health Organization Drug anatomical, therapeutic, chemical class and preferred term (PT). All concomitant medications administered will be presented in a data listing.

9.3.4. Safety Analyses

Safety analysis will be performed on the ITT population. Safety analyses in addition to those described in the following subsections may be performed at any time without prejudice, in order to most clearly enumerate rates of toxicities and to define further the safety profile of SL-901.

Treatment-Emergent Adverse Events

- AEs will be considered treatment-emergent (i.e., TEAEs) if they start on or after the time of the first dose of SL-901 and up to 30 days after the last dose of SL-901.
- TEAEs will be summarized by Medical Dictionary for Regulatory Activities (MedDRA™), Version 22 (or higher), system organ class (SOC) and PT. The severity of AEs will also be summarized by NCI CTCAE, Version 5.0 (or higher).
- Non-treatment-emergent AEs will be included in the patient listings and flagged as such but will not be included in the summary tables.
- Where an AE date is partial or missing, and it is unclear whether the AE is treatment-emergent, the AE will be assumed to be treatment-emergent.

Summary of TEAEs

The number and percentage of patients who experience TEAEs will be summarized overall by SOC and PT and will also be summarized based on severity and causality.

Descriptive analysis of AEs will include incidence of TEAEs and SAEs grouped by:

- SOC and PT
- SOC, PT and severity
- SOC, PT and causality
- SOC and PT leading to discontinuation from the study
- SOC and PT for events \geq Grade 3
- SOC and PT leading to death

Individual listings of all AEs will also be provided.

